### 7.3 Exploratory Efficacy Analyses

#### 7.3.1 Repeated Measures Analyses

To assess treatment as an effect over time on HbA1c change from baseline, a repeated measures analysis will be performed in supportive of the primary and secondary efficacy analyses. All observed measurements, excluding post-rescue measurements, of change from baseline in HbA1c through Week 96 will be included in the linear mixed effect model as repeated measures. Intercept and slope for time (entered as continuous variable) will be specified as random covariates, which may be simplified as fixed covariates depending on the assessment of the model fit. The PROC MIXED procedure in SAS will be used. The unstructured correlation for repeated HbA1c change from baseline will be specified; if the model fails to converge, an alternative correlation matrix will be specified.

As with HbA1c, repeated measures analyses will also be performed on change from baseline of body weight, systolic blood pressure, diastolic blood pressure, and FPG. A linear effect model will be utilized for each of the change from baseline measures similarly to that being used for HbA1c change from baseline. All analyses will be performed on the full analysis set.

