During the run-in period, subjects will be instructed to determine daily self-monitored blood glucose (SMBG) after an overnight fast. The SMBG record will be reviewed by the investigator at each clinic visit. If the fasting blood glucose is > 216 mg/dL (12 mmol/L) in two consecutive days, the subject should contact the clinical staff. In addition, subjects will be instructed that they must contact the clinic within 24 h if SMBG is ≥ 270 mg/dL (15 mmol/L). If the fasting SMBG is ≥ 270 mg/dL (15 mmol/L) without explanations for the elevation, the investigator will review the SMBG record and determine if the subject should attempt to improve diet and exercise to maintain glycemic control or if the subject must discontinue from the study and resume diabetic medications. Subjects with symptomatic hyperglycemia or hypoglycemia should be withdrawn if the symptoms are severe.

During the 24-week main treatment period, study subjects will be advised to continue daily SMBG measurements and contact the clinic if the SMBG is \geq 270 mg/dL (15 mmole/L) from week 1 (week of randomization) to week 6, \geq 240 mg/dL (13.3 mmole/L) from week 6 to week 12, or \geq 200 mg/dL (11.1 mmole/L) from week 12 to week 24. During the 72-week extension period (weeks 25 to 96), subjects will continue to monitor the SMBG and contact the clinic if SMBG is \geq 200 mg/dL (11.1 mmole/L). Values of HbA1c will be evaluated in the extension period by the investigator and approved standard of oral therapy will be prescribed if HbA1c is elevated.

The investigator must review the SMBG record and FPG values in every clinic visit and assess whether any subject should receive rescue medications to treat the hyperglycemic condition during the 24-week main treatment period. The subject must be queried to assess compliance with a minimum of a 10 h fast prior to blood draw to ensure the FPG values can be accurately determined. If a subject has not fasted for 10 h, the subject must return within a week after proper fasting. The investigator will provide diet and exercise counseling and determine if the subject should receive additional rescue medication as a result of the glucose. A serum sample must be drawn prior to the rescue medication so that the last HbA1c value while the subject is on study drug only can be carried forward to 24 weeks for the primary end point analysis.

OTHER SAFETY MONITORING ACTIVITIES

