9.5.2 Secondary Efficacy Endpoints

The secondary endpoints are considered exploratory and will not be corrected for multiplicity. The first secondary hypothesis is that EGT0001442 reduces FPG at weeks 2 and 24 when compared to controls. Change in FPG for each follow up visit will be estimated as follow-up minus baseline and the two treatment groups will be compared with two paired t-tests.

The second hypothesis is that EGT0001442 reduces the HbA1c to less that 7% of more patients when compared to placebo. HbA1c categories will be assessed for each patient as <7% or \geq 7% of each subject. The 2x2 contingency table of treatment by HbA1c category will be analyzed with a χ^2 test.

The third hypothesis is that EGT0001442 reduces blood pressure compared to placebo. Systolic and Diastolic blood pressure will be measured at baseline and at weeks 2 and weeks 24. Change in each blood pressure metric for both follow up visits will be estimated as follow-up minus baseline and the two treatment groups will be compared with four paired t-tests.

The fourth hypothesis is that EGT0001442 reduces body weight compared to placebo. Body weight will be measured at baseline and at weeks 2 and weeks 24. Change in body weight for both follow up visits will be estimated as follow-up minus baseline and the two treatment groups will be compared with two paired t-tests.

The final secondary hypothesis is that EGT0001442 induced change in HbA1c is evident over time, present at week 24 and maintained over the 96 weeks of the study. HbA1c is collected at baseline and weeks 2, 6, 12, 24, 36, 48, 60, 72, 84 and 96. Repeated measures of HbA1c will be analyzed with a linear mixed effect model to assess the overall treatment effect. Subsequently the change in each time point will be estimated as described for the primary endpoint and evaluated with 10 t-tests.

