### 3.4 Blinding, Randomization, and Bias

Eligible subjects who complete the  $14 \pm 3$  day run-in period and meet all study inclusion/exclusion requirements will be randomized in a 1:1 ratio to receive EGT0001442 20 mg/day or placebo according to a computer-generated randomization schedule. Subjects will be assigned to treatment groups in sequential order as they qualify for the study, using a centrally located and managed interactive web response system (IWRS). Randomization will be stratified by study center and screening HbA1c ( $\geq 7$  to < 8.5% or  $\geq 8.5$  to 10%). The study will be conducted at multiple investigative sites and will likely involve variable numbers of subjects at each site. Enrollment will be on a competitive basis but each site will be capped at 15% of the total randomized subjects (45 subjects).

The study drug will be blinded to the sponsor, investigators, study coordinators, pharmacists, study subjects, and the cardiovascular adjudication committee members. Upon randomization, each subject will receive a subject randomization number and drug kit(s) assigned to the subject. To maintain blinding of the treatment, the values of the HbA1c after dosing starts will remain blinded to all study personnel and subjects until all subjects have completed the 24 week treatment period. After all subjects have completed the 24 week treatment period, all previous and subsequent HbA1c values will be made available to the sponsor, investigators, study coordinators, pharmacists, and the study subjects for close monitoring of subjects' safety including assessment of providing rescue medication. Subjects' treatment assignment will continue to be held from all study personnel so the remainder of the study can be conducted in a blinded fashion.

If knowledge of the test substance is needed to manage the subject's condition, the investigator will contact the IWRS to obtain the treatment assignment. If unblinding occurs for any reason, the time and reason for unblinding will be recorded on the case report form (CRF) and the sponsor must be notified within 24 hours.

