### 3.5 Sample Size Justification

Approximately 300 subjects will be enrolled and equitably allocated to receive either EGT0001442 20 mg capsules or placebo.

The sample size of 150 subjects per group was calculated based on the following assumptions:

- The mean change from baseline to Week 24 in HbA1c in the active dose group will be approximately -0.4%.
- The placebo group will not experience a substantive mean change in HbA1c from baseline to week 24.
- The standard deviation of this change is the same for both groups and is 1.0%.
- The two groups are independent, the study design is balanced, and the two-sided significance level for the hypothesis is 0.05.

Under the above assumptions, an evaluable sample size of 133 evaluable subjects per treatment arm yields approximately 90% power that EGT0001442 treatment will be found to be significantly different from placebo. A sample size of 150 subjects per treatment arm will be enrolled to account for any subject lost-to-follow-up.

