#### 7.3.2 Analysis of Covariance

To assess treatment effect adjusted for important covariates on HbA1c change from baseline, an analysis of covariance (ANCOVA) model will be performed in supportive of the primary and secondary efficacy analyses. HbA1c change from baseline by visit will be analyzed using an ANCOVA model with treatment group, site (pooled as necessary), gender (male versus female), race (categorized as white, black, and other non-white), and age (categorized as <65 years, and ≥65 years) as factors and baseline HbA1c as a continuous covariate. One analysis will be performed using the LOCF algorithm for all visits, and a separate analysis will be performed using OC algorithm. The OC algorithm analysis will exclude any post-rescue values.

As with HbA1c, ANCOVA analyses will also be performed on change from baseline of body weight, systolic blood pressure, diastolic blood pressure, and FPG. For each of these endpoint, the ANCOVA model will include treatment group, site (pooled as necessary), gender (male versus female), race (categorized as white, black, and other non-white), age (categorized as <65 years, and ≥65 years), and baseline HbA1c category (≥7 to <8.5% versus ≥8.5 to ≤10%) as factors and corresponding baseline endpoint measures (i.e., baseline FPG for FPG change from baseline ANCOVA mode) as a continuous covariate. All analyses will be performed on the full analysis set.

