 $\ensuremath{\texttt{[1]}}$  Based on repeated measure model including treatment and visit as factors.

Protocol: THR-1442-C-418 Page x of y

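### The exploratory repeated-measures models omit the baseline value that the SAP's own ANCOVA includes, which can cost precision and slightly weakens the missing-at-random assumption for long-term HbA1c

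*SAP*

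**What the plan says.** SAP 7.3.1, under the exploratory efficacy analyses, plans a mixed model: "All observed measurements, excluding post-rescue measurements, of change from baseline in HbA1c through Week 96 will be included in the linear mixed effect model". The text names an intercept and a slope for continuous time and offers the analysis as support for the primary and secondary results. The HbA1c shell, Table 14.2-1.4, describes the model in footnote [1]: "Based on repeated measure model including treatment and visit as factors". Tables 14.2-2.4, 3.4, 4.4 and 5.4 repeat that footnote for FPG, weight, systolic and diastolic blood pressure. None of these places names baseline or the HbA1c stratum.

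Elsewhere the SAP does use both. The HbA1c ANCOVA in 7.3.2 takes treatment, site, gender, race and age "as factors and baseline HbA1c as a continuous covariate". For the other endpoints it uses their own baseline plus the HbA1c category. On allocation, SAP 3.4 says: "Randomization will be stratified by study center and screening HbA1c".

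Two further rules matter. SAP 5.3.2 handles post-rescue efficacy values as missing. Protocol 3.1 says that in the extension "approved standard of oral therapy will be prescribed if HbA1c is elevated", with no numeric threshold.

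**The concern.** The outcome is a change score, and its baseline is usually its strongest predictor. Leaving baseline out puts explainable variation into the error term. It also makes adjacent sections of the SAP inconsistent, and no reason is given.

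The second issue is missing data. A likelihood-based mixed model that drops post-rescue values relies on missing-at-random, given what the model contains. In the extension the decision to add therapy looks at the HbA1c level, which is baseline plus change. A model that holds only changes does not contain everything that decided the removal, even when the decision rests entirely on observed values. With baseline in the model, missing-at-random becomes more credible.

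At stake is the accuracy of the long-term HbA1c difference reported in Table 14.2-1.4, and the precision of all five models.

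**Working it through.** **1. The plan's own figure.** SAP 3.5 assumes a difference of 0.4, an SD of change of 1.0, and "the two-sided significance level for the hypothesis is 0.05". It concludes that "an evaluable sample size of 133 evaluable subjects per treatment arm yields approximately 90% power".

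n per arm = 2 × (1.960 + 1.282)² × 1.0² / 0.4² = 131.4, so 132. By the normal approximation, power is 90.4% at 133 per arm and 89.9% at 131, the figure in Protocol 9.2. The plan's figure is reproduced. It belongs to the Week 24 t-test; no figure is given for the repeated-measures models.

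**2. Precision.** With baseline in the model and complete data, SE = SD × √(1 − r²) × √(2/n), where r is the baseline–change correlation. At n = 133, √(2/133) = 0.123.

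| \|r\| | √(1 − r²) | SE | SE reduction | Power for 0.4 |
|---|---|---|---|---|
| 0 | 1.000 | 0.123 | 0% | 90.4% |
| 0.2 | 0.980 | 0.120 | 2% | 91.5% |
| 0.3 | 0.954 | 0.117 | 5% | 92.8% |
| 0.4 | 0.917 | 0.112 | 8% | 94.5% |
| 0.5 | 0.866 | 0.106 | 13% | 96.5% |

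The documents do not give r. If baseline and follow-up HbA1c had the same SD s, then r = −SD(change)/(2s). With SD(change) = 1.0 and an assumed s of 0.9 to 1.2, r is −0.56 to −0.42. Zero is still possible: with a baseline SD of 0.9 it needs a follow-up SD of √(0.81 + 1.0) = 1.35.

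**3. Shift at Week 96 for HbA1c.** Two simulations used 11 visits, unstructured covariance and a true difference of −0.40. Values were removed once HbA1c first reached a threshold. Correlations and thresholds are assumptions. Both simulations include a treatment-by-visit term, so that only the effect of baseline differs between columns.

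| Simulation | r | Threshold | Without baseline | With baseline-by-visit | Shift |
|---|---|---|---|---|---|
| A | −0.3 | 9.5% | −0.416 | −0.393 | 0.023 |
| A | −0.3 | 9.0% | −0.418 | −0.388 | 0.030 |
| A | −0.5 | 9.5% | −0.431 | −0.394 | 0.037 |
| A | −0.5 | 9.0% | −0.442 | −0.392 | 0.050 |
| B | −0.21 | 9.0% | −0.414 | −0.400 | 0.014 |
| B | −0.21 | 8.5% | −0.430 | −0.413 | 0.017 |
| B | −0.41 | 9.5% | −0.403 | −0.389 | 0.014 |
| B | −0.41 | 9.0% | −0.415 | −0.391 | 0.024 |
| B | −0.41 | 8.5% | −0.429 | −0.395 | 0.034 |

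A is 400 trials of 133 per arm, with an assumed baseline SD of 0.9 and 15% random dropout; the Monte Carlo SE of the shift is 0.002 to 0.003. B is a single large sample of 40,000 per arm.

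The shift is measured against the adjusted estimate. Against the true −0.40, the unadjusted error in A is 0.016 to 0.042. In B the shift is zero at r = 0, at most 0.003 with no treatment effect, and 0.01 to 0.03 if the true effect fades to −0.10.

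**4. Precision under removal.** In A the ratio of squared SEs, with to without baseline, is 0.905 and 0.912 at r = −0.3, and 0.769 and 0.797 at r = −0.5. In B at r = −0.41 and a 9.0% threshold, the SE at 150 per arm falls from 0.167 to 0.159, about 5%.

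**5. The stratum.** In B, adding the HbA1c stratum on top of continuous baseline moves the HbA1c estimate by less than 0.001.

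**6. The model as the shell states it.** With treatment and visit main effects only, no missing data and r = 0, B gives −0.13 against a true −0.40. Baseline plays no part in that error; it comes from the absent treatment-by-visit term, and its size depends on the assumed onset and variances.

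**The case against.** A reader might infer that the model as written biases the Week 96 result toward the drug. The documents do not support that. The shifts above belong to a model with a treatment-by-visit term, which neither SAP 7.3.1 nor the shell names. In the main-effects model, a further check found that adding baseline-by-visit moved the estimate by at most about 0.02, in either direction.

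The simulated removal rule is also cruder than the plan. Before Week 24, rescue is assessed from self-monitored and fasting glucose (Protocol 3.1), and post-dose HbA1c stays blinded until all subjects finish Week 24 (SAP 3.4). Baseline HbA1c does not fully capture glucose-triggered rescue. Starting removal at Week 24 gave shifts of 0.02 to 0.04 in the interaction model, within the range above.

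A reader might also take this model as the decisive test that the effect lasts to Week 96. Protocol 9.5.2 gives it a different task: "Repeated measures of HbA1c will be analyzed with a linear mixed effect model to assess the overall treatment effect". Individual time points then go to t-tests. SAP 7.2.1 makes the by-visit t-tests the secondary analysis, and SAP 5.2 gives secondary and exploratory results nominal p-values only.

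Finally, the 7.3.2 ANCOVA runs at every visit on observed pre-rescue values, to Week 96 and beyond (Table 14.2-1.3), so a baseline-adjusted Week 96 difference will be available. This lowers the stakes but does not remove the point. That ANCOVA uses only subjects still observed and unrescued at each visit, whereas the mixed model uses partial trajectories.

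All of these limits stand. The omission of baseline, and its inconsistency with 7.3.2, are not answered by them.

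**Conclusion.** The point holds as an efficiency and consistency defect in an exploratory analysis. The precision loss is real if baseline correlates with change: about 5% of the SE at |r| = 0.3, 13% at 0.5, none at 0. For HbA1c, omitting baseline makes missing-at-random less credible and can move the Week 96 difference by about 0 to 0.05 points toward the drug. That range depends on correlations and thresholds the documents do not give, and on a treatment-by-visit term being present. It would matter most in relative terms if the true effect had faded.

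The shift was not calculated for FPG, weight or blood pressure, and the argument about removal by HbA1c level does not carry over to weight or blood pressure. For those endpoints the case is precision and agreement with 7.3.2. A reader might infer that the missing stratum is itself a fault in the HbA1c model; once continuous baseline HbA1c is included, it adds nothing material there.

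The primary test is unaffected.

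**What to change.** In SAP 7.3.1 and footnote [1] of Tables 14.2-1.4, 2.4, 3.4, 4.4 and 5.4, add the baseline value of the endpoint as a continuous covariate, with a baseline-by-visit term. For FPG, weight, systolic and diastolic blood pressure, also add the HbA1c stratum in line with 7.3.2. State whether that means the screening stratum used for randomization or the baseline category named in 7.3.2.

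The cost is SAP wording, a few model terms and a few degrees of freedom (up to 11 for baseline-by-visit). No new data or subjects are needed. The reported long-term difference may become slightly smaller.

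In the same edit, resolve the separate and larger defect of the missing treatment-by-visit term, and reconcile continuous time in 7.3.1 with visit as a factor in the shells.

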#### 7.3.2 Analysis of Covariance

To assess treatment effect adjusted for important covariates on HbA1c change from baseline, an analysis of covariance (ANCOVA) model will be performed in supportive of the primary and secondary efficacy analyses. HbA1c change from baseline by visit will be analyzed using an ANCOVA model with treatment group, site (pooled as necessary), gender (male versus female), race (categorized as white, black, and other non-white), and age (categorized as <65 years, and ≥65 years) as factors and baseline HbA1c as a continuous covariate. One analysis will be performed using the LOCF algorithm for all visits, and a separate analysis will be performed using OC algorithm. The OC algorithm analysis will exclude any post-rescue values.

As with HbA1c, ANCOVA analyses will also be performed on change from baseline of body weight, systolic blood pressure, diastolic blood pressure, and FPG. For each of these endpoint, the ANCOVA model will include treatment group, site (pooled as necessary), gender (male versus female), race (categorized as white, black, and other non-white), age (categorized as <65 years, and ≥65 years), and baseline HbA1c category (≥7 to <8.5% versus ≥8.5 to ≤10%) as factors and corresponding baseline endpoint measures (i.e., baseline FPG for FPG change from baseline ANCOVA mode) as a continuous covariate. All analyses will be performed on the full analysis set.

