4.2 Inclusion Criteria

- 1. Male or female subjects ≥18 years old
- 2. Diagnosed with type 2 diabetes
- 3. Body mass index (BMI) \leq 37 kg/m²
- 4. HbA1c between 7 and 10% (inclusive) at screening based on an upper limit of normal for the HbA1c assay being 6.5±0.2 %
- 5. FPG <250 mg/dL at screening for subjects not treated with oral anti-diabetic therapies or FPG <240 mg/dL at screening for subjects treated with anti-diabetic therapies
- 6. Diabetes currently treated with diet and exercise only or diet and exercise along with one approved oral anti-diabetic agent
- 7. If taking anti-diabetic medication, dose and regimen must be stable for past 3 months
- 8. If taking antihypertensive medication, dose and regimen must be stable for past 3 months
- 9. If taking lipid modifying therapy, dose and regimen must be stable for past 3 months
- 10. Blood glucose <250 mg/dL based on finger stick blood glucose for all subjects at randomization
- 11. Subjects willing and able to comply with the investigational nature of the study and able to communicate well with investigators.
- 12. Able to comprehend and willing to provide written informed consent in accordance with institutional and regulatory guidelines.

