7.1.2 Visit 2 – run-in period (day -14±3)

- Confirm eligibility
- Diet and exercise counseling
- Glucometer dispensing and training for SMBG determination
- Discontinue anti-diabetic medication
- Vital Signs: blood pressure, pulse, temperature, respiratory rate taken in the sitting position after at least 5 minutes of rest. Blood pressure must be measured twice with at least 3 min apart

Dispense study medication for the run-in period

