9 PLANNED STATISTICAL METHODS

9.1 General Considerations

The primary objective of this trial is to assess the efficacy of EGT0001442 in treatment-naïve type-2 diabetic patients or patients on a single oral anti-diabetic drug in combination with diet and exercise with an HbA1c between 7 and 10%. Efficacy, in this case, is defined as a significant reduction in HbA1c at week 24 when compared to placebo. The effect of EGT0001442 on fasting glucose, blood pressure, body weight and the general safety of EGT0001442 in patients with T2DM will also be explored.

Statistical analyses and summaries of safety and tolerability will be performed using SAS® software (SAS Institute, Cary, NC). In all cases, significance will be judged at the α =0.05 level. No multiplicity adjustment will be required for the single primary endpoint.

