## 3 Study Design

### 3.1 Brief Description

THR-1442-C-418 is a multinational, 2 arm parallel group, randomized, double-blind placebo-controlled study to compare treatment with once daily EGT0001442, 20 mg capsules to matching placebo in either treatment-naïve type 2 diabetic subjects (i.e. those not taking an anti-hyperglycemic agent for ≥16 weeks prior to study entry) or subjects treated with one oral anti-diabetes drug. The study design consists of a screening period, a 2-week placebo run-in (washout) period, and a 96-week double-blind treatment period. The primary analysis will take place after 24 weeks of double-blind treatment.

In the proposed study, diabetic subjects will be screened within 3 weeks of washout start. At screening visit, subjects who meet all the inclusion criteria, none of the exclusion criteria, and who consent to participate in the study will receive counseling for appropriate diet and exercise. Those who are on an oral anti-diabetic medication will discontinue the medication and receive placebo in this run-in period for  $14 \pm 3$  days. Eligible diabetic subjects who are treatment naïve and who control their hyperglycemia through diet and exercise will also receive placebo and the hyperglycemia will be monitored to ensure that their fasting blood glucose levels remain below 250 mg/dL during this interval of  $14 \pm 3$  days.

After the run-in period, approximately 300 subjects will complete the baseline assessment on day 1, after overnight fasting to confirm their eligibility. The subjects that remain eligible will be randomly assigned in a 1:1 ratio to receive either once daily EGT0001442 in 20 mg capsules or matching placebo, using a computer-generated allocation schedule. Randomization will be stratified by study center and screening HbA1c ( $\geq$ 7 to <8.5% or  $\geq$ 8.5 to  $\leq$ 10%). Each subject will be provided with study drug for 24 weeks, dosing instructions, diet and exercise counseling, and a glycemic control card for recording food and fasting glucose information on the days prior to each clinic visit

Each subject will be instructed to return to the clinic on weeks 2, 6, 12, 18, and 24 for safety monitoring and efficacy assessment including review of adverse events, concomitant medication, vital signs, ECG, physical examination, testing of blood chemistry and hematology laboratory parameters, and a urinalysis.

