#### 5.3.1 Last Observation Carried Forward

Imputation for missing observations will be applied to selected efficacy endpoints by using the last observation carried forward method. For subjects who withdraw from the study, the last valid observation recorded on treatment (scheduled or unscheduled) will be carried forward to all remaining visits. Also, for subjects in efficacy analyses who had missing observations prior to their last observation on treatment, the closest previous non-missing on-treatment observation will be carried forward to missing visits. If a subject had missing observation(s) immediately after baseline, the baseline observation will not be carried forward and the visit(s) will be left as missing.

In general, the LOCF method will be used for all efficacy endpoints that are evaluated at or before Week 24. Beyond Week 24, all analyses will not impute any missing data; this non-imputation method will be referred to as the observed case (OC). The descriptive summaries of endpoints by study medication group will include the count of missing values at each visit. The detail of which analysis utilizes LOCF algorithm is available in Section 7.

It is expected that 24 weeks of treatment is required to obtain the full treatment effect; shorter treatment periods may result in the observation of only a partial (smaller) treatment effect. Therefore, assuming that subject discontinuation of study drug or early termination from study will occur equally and at random in both treatment groups and in each stratum, this LOCF imputation approach is expected to provide a statistically conservative estimate for the treatment effect.

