### Table 14.1-2.2 Diabetes Disease History (Safety Analysis Set)

	EGT0001442 (N=xxx)	Placebo (N=xxx)
Duration of Diabetes (years) [1]		
n	xxx	xxx
Mean (SD)	xx.x (xx.xxx)	xx.x (xx.xxx)
Median	xx.x	xx.x
Min, Max	xx, xx	xx, xx
Baseline Diabetes Therapy		
n	xxx	XXX
Treatment Naive	xxx (xx.x%)	xxx (xx.x%)
Treated with One Anti-diabetic Agent	xxx (xx.x%)	xxx (xx.x%)
Blindness		
n	xxx	xxx
Yes	xxx (xx.x%)	xxx (xx.x%)
No	xxx (xx.x%)	xxx (xx.x%)
Cataracts		
Retinopathy		
Laser Treatment to Either Eye		
Foot Ulceration		
Peripheral Neuropathy		
Lower Limb Amputation		
Diabetic Nephropathy		
Current Microalbuminuria		
Current Proteinuria		
Dialysis		
Kidney Transplantation		
Major Hypoglycemic Event		
Documented Hypoglycemic Event		

 To calculate duration from a partial diagnosis date, a missing month is imputed as January and a missing day is imputed as the first of the month.

Source Data: Listings 16.2-4.4 and 16.2-4.5

Protocol: THR-1442-C-418 Page x of y

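### Prior diabetes therapy (naive, or withdrawn from one oral agent about two weeks before baseline) is collected but enters no efficacy model or subgroup

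*SAP*

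**What the plan says.** Protocol 9.1 states the aim as to "assess the efficacy of EGT0001442 in treatment-naïve type-2 diabetic patients or patients on a single oral anti-diabetic drug". SAP 3.1 defines the naive group as "those not taking an anti-hyperglycemic agent for ≥16 weeks prior to study entry". The other group must have been on a stable regimen for three months (Protocol 4.2, criterion 7). At Visit 2 the instruction is "Discontinue anti-diabetic medication" (Protocol 7.1.2). Visit 3 follows 14 ± 3 days later, and the SAP shells take baseline as the last value up to the first dose.

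The information is recorded. Protocol 9.4 lists naive status among the baseline characteristics. SAP Table 14.1-2.2 has a naive row and a row labelled "Treated with One Anti-diabetic Agent", by arm, in the safety set. SAP 6.2 does not carry it into the main baseline table.

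For the supportive adjusted analysis of HbA1c, SAP 7.3.2 specifies an "ANCOVA model with treatment group, site (pooled as necessary), gender (male versus female), race (categorized as white, black, and other non-white"). The sentence goes on to add age category as a factor and baseline HbA1c as a continuous covariate. That section says its purpose is to adjust for important covariates.

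**The concern.** The two groups can be expected to behave differently after Day 1. A subject off all agents for at least 16 weeks is plausibly near a stable HbA1c. A subject who stopped an agent two weeks ago may still be losing its effect, so HbA1c may rise during the 24 weeks in either arm. Baseline HbA1c does not capture this, because a naive and a just-withdrawn subject can share a baseline value and then diverge.

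Four things are at stake:

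- extra between-subject variance in the Week 24 change;
- chance imbalance in prior therapy that no model corrects;
- within-arm changes, at every visit, that combine drug effect with loss of the old drug;
- no reported estimate in either of the two populations that the objective names.

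**Working it through.** **Which analyses use prior therapy**

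- Randomisation strata (SAP 3.4): centre and screening HbA1c only.
- Primary analysis (SAP 7.1): unadjusted two-sample t-test.
- HbA1c below 7% (SAP 7.2.5): unadjusted chi-square test.
- Repeated measures (SAP 7.3.1; shell 14.2-1.4): the shell lists treatment and visit; prior therapy is in neither place.
- ANCOVA (SAP 7.3.2; footnotes to the 14.2 shells): not included, for HbA1c or the other endpoints.
- Sensitivity analyses (SAP 7.3.3): the same t-test and ANCOVA in the per protocol set.
- Subgroups: none in the text or the shells.

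**The plan's own figure.** Inputs from SAP 3.5: difference 0.4, SD 1.0, two-sided alpha 0.05, power 90%. The normal approximation n = 2(1.960 + 1.282)²(1.0/0.4)² gives 132 per arm; the noncentral t gives 133. Power is 90.1% at 133 (SAP) and 89.7% at 131 (Protocol 9.2). Both stated sizes reproduce, and this point does not contest them.

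**Assumed inputs.** Let p be the share previously on an oral agent and d the extra drift in that group. The documents give neither. I take p = 0.3 to 0.7 and d = 0.3 to 1.0 HbA1c points.

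**Is the between-arm difference biased?** Simulation, 20,000 runs per scenario, 133 per arm, p = 0.5, d = 0.5, residual SD 1.0, no dropout or rescue:

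- Unadjusted t-test: mean difference −0.399 for a true −0.400; type I error 4.9%; power 88.4%.
- With a prior-therapy term: power 90.2%.

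Drift that occurs in both arms cancels in expectation. What it costs is precision.

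**Precision, if the total SD of 1.0 already includes drift.** Share of variance explained = p(1−p)d².

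- Low: 0.3 × 0.7 × 0.3² = 0.0189; residual SD = √0.9811 = 0.991; interval about 1% narrower.
- High: 0.5 × 0.5 × 1.0² = 0.25; residual SD = √0.75 = 0.866; interval about 13% narrower.

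This gain belongs to the adjusted analysis. It would be smaller if terms already in the ANCOVA carry part of the drift.

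**If instead the SD of 1.0 excludes drift.** The unadjusted SD becomes √1.0189 = 1.009 to √1.25 = 1.118, and t-test power at 133 per arm is 89.6% to 82.8%. The documents do not say which case applies.

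**Chance imbalance.** A one-SD imbalance at 150 per arm shifts the difference by d√(2p(1−p)/150):

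- Low: 0.3 × √(0.42/150) = 0.016.
- High: 1.0 × √(0.50/150) = 0.058.

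The standard error of the difference is √(2/150) = 0.115. A 10-percentage-point imbalance would shift it by 0.1d = 0.03 to 0.10, against a planned effect of 0.4.

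**Within-arm change.** Drift adds p × d to each arm's mean: 0.3 × 0.3 = 0.09 to 0.7 × 1.0 = 0.70 points. SAP 3.5 assumes no substantive change on placebo.

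**What a split by prior therapy could show.** With an even split (75 per cell), the interaction has SE √(4/75) = 0.231. Power for an interaction of 0.4 is Φ(0.4/0.231 − 1.96), about 41%. With 45 per arm (p = 0.3), power for the 0.4 effect within that group is Φ(0.4/√(2/45) − 1.96), about 47%.

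**The case against.** The primary comparison is randomised and unadjusted, drift occurs in both arms, and chance imbalance is ordinary sampling variation that the t-test's interval already covers. Prior therapy is tabulated by arm, so an imbalance would be seen. Baseline HbA1c is in the ANCOVA and screening HbA1c is a stratum. All of this stands. It confines the point to supportive analyses and reporting; it does not give a reason to leave a recorded and plausibly prognostic factor out of them.

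A reader might draw four stronger conclusions that the documents do not support.

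- **The primary result is contaminated by drift.** It is not, for the reason the simulation shows. The simulation does not cover the rule that carries HbA1c forward from rescue or dropout. If rescue differed between arms, that rule could cut drift short unequally. The documents give no rates, and I make no claim on it.
- **Adjustment raises the power of the primary test.** The primary stays a t-test, so its power is unchanged.
- **The SAP's own time scales show that baseline still carries most of the old drug's effect.** SAP 5.3.1 says "It is expected that 24 weeks of treatment is required to obtain the full treatment effect", but this concerns the study treatment and is given to justify carrying values forward. The 16 weeks is an entry definition. Neither says how much effect remains two weeks after stopping.
- **The trial makes an add-on claim.** Protocol 9.1 does speak of "patients on a single oral anti-diabetic drug in combination with diet and exercise", but the formal objective in Protocol 2.1 makes no such claim and withdrawal is explicit elsewhere. This is a wording conflict.

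The 16-week definition is likewise missing from the inclusion list, where criterion 6 reads "Diabetes currently treated with diet and exercise only or diet and exercise along with one approved oral anti-diabetic agent". The protocol supplied is the original of 02 February 2011, however. The SAP shell for Table 14.1-1.3 cites versions dated 2011-04-11, 2011-08-18 and 2011-09-12, so the list may have changed.

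**Conclusion.** The omission is real: prior therapy is recorded, plausibly prognostic, and used in no efficacy analysis. The randomised comparison stays valid. The size rests entirely on the assumed share and drift. At the low end the gain in precision is negligible; at the high end the adjusted interval is about 13% narrower. The firmer argument does not depend on those assumptions: the plan names two populations and reports the effect in neither. The sample size cannot demonstrate efficacy separately in each, so estimates by prior therapy would be descriptive. I class this as an improvement at almost no cost. It does not correct an error in the primary inference.

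**What to change.** - Add baseline diabetes therapy (naive or one oral agent, from the field behind Table 14.1-2.2) as a factor in the SAP 7.3.2 ANCOVAs, the 7.3.1 repeated-measures models and the matching shell footnotes. Leave the primary t-test as it is.
- Add one table with the Week 24 HbA1c difference and confidence interval by prior therapy, and the treatment-by-prior-therapy interaction estimate, labelled descriptive.
- Reconcile the description of the population in Protocol 9.1 and the synopsis with the withdrawal at Visit 2, and the 16-week definition in Protocol 3.1 and SAP 3.1 with the current inclusion list. Which eligibility rule applies is for the sponsor to settle.

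The cost is one model term, one table and some wording, with no new data. The changes should be made before unblinding for the Week 24 analysis.
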